## 6.1.4 Compliance to Treatment regimen

# PPD

Subject will be considered compliant to study treatment regimen if conditions defined in section 6.1.1.3, 6.1.2.3 and 6.1.3.3 are met (i.e. subject compliant to global criteria regarding IMP intake, ON-treatment period, OFF-treatment period).

Overall compliance to treatment regimen will be presented (Y/N) by treatment and overall.

## 6.1.5 Started Cycles

Per each subject the number of cycles started during the entire treatment period will be counted. The  $i$ -th cycle is defined as started if at least 1 IMP intake is reported in the cycle (Data start Cycle ( $i$ ) is not missing).

The number of started cycles over the entire treatment period will be summarized by treatment and overall by means of summary statistics.

A listing of information about IMP ACCOUNTABILITY and IMP DISPENSATION will be provided by cycle and overall.

A listing will also be produced by reporting all detail regarding compliance criteria described above by cycles and overall.

## 6.2 Exposure to IMP

The extent of exposure to IMP in weeks will be summarized overall with descriptive statistics by treatment group. The extent of exposure (weeks) will be calculated using the formula reported in Table 3.

## 7. Evaluation of Efficacy

All analyses will be considered descriptive in nature. No multiplicity correction of type I error is required.

### 7.1 Analysis of primary endpoint

Number and proportion along the 95% confidence interval (Clopper-Pearson's formula) of patients with HbA1c < 7% and daily insulin requirement <0.5 (IU/kg/day) will be calculated at Month 12. The comparison between the two study treatment arms will be performed by means of a Chi-square test or, if more appropriate, a Fisher's Exact test at each time point.

### 7.2 Analysis of secondary efficacy endpoints

# PPD

All secondary endpoints will be analysed at each available time point by means of descriptive statistics as detailed in sections 7.2.1.1-7.2.1.10.

The following results will be displayed graphically:

- The proportion at each time point by treatment of patients with HbA1c <7% and daily insulin requirement <0.5 (IU/kg/day);
- The means ( $\pm$ SEs) at each time point by treatment of the HbA1c and its change from baseline;
- The proportion at each time point by treatment of patients with HbA1c of less than 7% who did not experience severe hypoglycemic events during treatment;
- The means ( $\pm$ SEs) at each time point by treatment of the daily insulin requirement (IU/kg/day);
- The means ( $\pm$ SEs) at each time point by treatment of the 2-hour AUC of C-peptide post MMTT and its change from baseline;
- The means ( $\pm$ SEs) at each time point by treatment of the TIR by CGM and its change from baseline.

In each graph, where possible, significant p-values from the below analyses will be reported in the plot area, in correspondence of the associated time point.

#### *7.2.1.1 Proportion of patients with HbA1c <7% and daily insulin requirement <0.5 (IU/kg/day)*

Number and proportion along the 95% confidence interval (Clopper-Pearson's formula) of patients with HbA1c < 7% and daily insulin requirement <0.5 (IU/kg/day) will be calculated for each time point. The comparison between the two study treatment arms will be performed by means of a Chi-square test or, if more appropriate, a Fisher's Exact test at each time point.

#### *7.2.1.2 Proportion of patients with a reduction in HbA1c >0.5% from baseline and daily insulin requirement <0.50 IU/Kg/day*

Number and proportion along the 95% confidence interval (Clopper-Pearson's formula) of patients with a reduction in HbA1c > 0.5% from baseline and daily insulin requirement <0.5 (IU/kg/day) will be calculated for each time point. The comparison between the two study treatment arms will be performed by means of a Chi-square test or, if more appropriate, a Fisher's Exact test at each time point.

#### *7.2.1.3 2-hour AUC of C-peptide response to the MMTT*

2-hour AUC of C-peptide post MMTT and its change from baseline will be summarized at each available timepoint and comparison between treatments will be performed by means of two-sample t-test or, if assumptions of normality are not confirmed (by Kolmogorov-Smirnov test), two-sample Mann-Whitney U test.

#### *7.2.1.4 Time in range (TIR) by CGM*

TIR by CGM and its change from baseline will be summarized at each available timepoint and comparison between treatments will be performed by means of two-sample t-test or, if

# PPD

assumptions of normality are not confirmed (by Kolmogorov-Smirnov test), two-sample Mann-Whitney U test.

## 7.2.1.5 *HbA1c levels*

HbA1c and its change from baseline will be summarized at each available timepoint and comparison between treatments will be performed by means of two-sample t-test or, if assumptions of normality are not confirmed (by Kolmogorov-Smirnov test), two-sample Mann-Whitney U test.

## 7.2.1.6 *Proportion of patients with HbA1c <7% who did not experience severe hypoglycemic events during treatment*

Number and proportion along the 95% confidence interval (Clopper-Pearson's formula) of patients with HbA1c < 7% and absence of episodes of severe hypoglycemia during treatment will be calculated for each time point. The comparison between the two study treatment arms will be performed by means of a Chi-square test or, if more appropriate, a Fisher's Exact test at each time point.

The proportion of patients with HbA1c <7% is calculated at timepoint level: number of events occurring at a specific timepoint.

Severe hypoglycemic events are considered cumulatively and only event up to month 12 will be considered (condition will be evaluated by considering treatment period only).

In particular:

- if a subject experienced the event at a specific timepoint, it will be considered as a subject with the event for all subsequent timepoints.

## 7.2.1.8 *Number of self-reported episodes of severe hypoglycemia*

The effect of treatment on the cumulative number of severe hypoglycemic events will be evaluated by means of a Cox proportional hazards model. The Andersen-Gill intensity model with model-based variance will be utilized. The corresponding SAS code is provided in Appendix 12.2.

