#### 9.5.2.2. Secondary analyses

All secondary endpoints will be analyzed at each available timepoints by means of descriptive statistics and by appropriate parametric tests depending on the nature of the variable and its distribution. Data transformation might be used in order to satisfy the assumption of normality requested by parametric statistical tests. In case such assumptions are not met, non-parametric counterpart tests will be used. Details will be provided in the SAP. Change from baseline value (for continuous variables) and shift tables versus baseline (for categorical variables) will also be summarized for all post-baseline visits.

Additional analyses will include the analysis of the AUCs, daily insulin requirements and HbA1c values by repeated measurements models. The adjusted least squares means will be estimated for each combination of time point and treatment. The tests of the fixed effects will be presented, together with the estimated least squares means. The estimated treatment difference between ladarixin and placebo at each time point will be presented together with the corresponding 95% confidence interval.

The effect of treatment on the cumulative number of severe hypoglycemic events will be evaluated using an Andersen-Gill analysis with robust sandwich-type variance estimate.

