### 3.6.2 Secondary efficacy endpoints

The secondary efficacy endpoints are the following:

- Proportion of patients with HbA1c <7% and daily insulin requirement <0.50 IU/Kg/day at Month 6 and 18;
- Proportion of patients with a reduction in HbA1c > 0.5% from baseline and daily insulin requirement <0.50 IU/Kg/day at Month 6, 12, and 18;
- 2-hour Area Under the Curve (AUC) of C-peptide response to the Mixed Meal Tolerance Test (MMTT) at Month 6, 12, and 18;
- Time in range (TIR) by Continuous Glucose Monitoring (CGM) at Month 6, 12, and 18;
- HbA1c levels at Month 6, 12, and 18;
- Proportion of patients with HbA1c <7% who did not experience severe hypoglycaemic events during treatment at Month 6, 12, and 18;
- Additional Glucose Variability Indices derived from CGM at Month 6, 12, and 18;
- Number of self-reported episodes of severe hypoglycaemia at Month 6, 12, and 18;
- Average (previous 3 days) daily insulin requirements (IU/kg/day) at Month 6, 12, and 18;
- Estimated Glucose Disposal Rate (eGDR) at Month 6, 12, and 18;

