## 4.8 Changes in the planned analysis

Due to the company decision to stop the enrolment, fewer patients compared to the originally planned will be available for the analysis. Thus, the following changes were implemented:

- one single final analysis is planned after DB lock;

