# PPD

Summary statistics of blood glucose level (mg/dL) will be provided by treatment arm at each time point for patients reporting severe hypoglycemia. Derivation of patients reporting severe hypoglycemia will be the same as the one described in 7.2.1.6 section, except that in this case events happened between month 12 and month 18 will be considered as well.

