# PPD

## 10. Tables, Figures and Listings

### 10.1 Output conventions

- Each Table, Listing and Figure (TFL) should be numbered, if applicable, following the ICH E3 guideline.
- All tables/figures/listings will be presented in landscape format.
- The standard font size is 9 points “Courier New” for all tables. Listings will be presented with an 8 or 7 points Arial.
- Titles will be center-aligned; footnotes will be left-aligned.
- Each table/figure/listing will have 2 titles:
  - The 1st title will be the table/figure/listing number with the description of the table/figure/listing;
  - The 2nd title will be a description of the study set presented in the table/figure/listing.
- Some tables will have a third title (before 2nd title) with a description of the statistical method used in those tables.
- Any footnote added to explain the table/listing/figure contents will be presented in the following format:
  - Note 1: ...
  - Note 2: ...
  - Note 3: ...
- In the tables, listing and figures the treatment under comparison will be labelled as “Ladarixin” and “Placebo”
- Missing descriptive statistics or p-values which cannot be estimated are reported as “-”.
- The last two footnotes of each table/figure will be footers indicating:
  - the reference listing of the data;
  - the program name, the date and time of generation and the SAS® version used.
- Unless otherwise stated, listings will be presented by randomised treatment, and sorted by the treatment group, patient number, and visit.
- In all the listings on safety variables, a column with a flag (\$) for treatment misallocation will identify the treatment misallocations.
- The derived variables will be identified in the listings with a flag (\*).
- In general, dates will be presented on listings in the format ddmmmyyyy (date9.) and time in the format hh:mm (time5.). In case of partial dates or times, missing information will be replaced by dashes.
- Numeric variables will be listed generally with the same number of decimal places as in the actual data; units will be presented enclosed in square brackets ([ ]), when appropriate.

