# PPD

## 12.2 SAS code for Andersen-Gill intensity model

The following SAS code will be used to implement Andersen-Gill intensity model:

```
title 'Intensity Model';
proc phreg data=dataset covm ;
    class trt01pn (ref="2");
    model (Tstart, Tstop) * status (0) = trt01pn;
    hazardratio trt01pn;
run;
```

- The *covm* option specifies that the model-based covariance matrix will be used
- In *Ref* option the Placebo group should be specified
- a *TStart* variable to represent the  $(k - 1)$  recurrence time or the value 0 if  $k = 1$
- a *TStop* variable to represent the  $k$ th recurrence time or the follow-up time if  $k = K + 1$
- a *Status* variable indicating whether the *TStop* time is a recurrence time or a censored time; for example, *Status*=1 for a recurrence time and *Status*=0 for censored time

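### The number of severe hypoglycaemic episodes is compared only by an unpenalised Cox hazard ratio, which is uninformative if one arm has no episodes, and SAP 7.2.1.8 names no count or rate to fall back on

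*SAP*

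**What the plan says.** SAP 3.6.2 lists the endpoint as "Number of self-reported episodes of severe hypoglycaemia at Month 6, 12, and 18".

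SAP 7.2.1.8 gives one between-arm analysis of that number: "The effect of treatment on the cumulative number of severe hypoglycemic events will be evaluated by means of a Cox proportional hazards model". It adds: "The Andersen-Gill intensity model with model-based variance will be utilized". The code in Appendix 12.2 has treatment as the only model term and the statement "hazardratio trt01pn". It requests no penalty, no profile-likelihood limits and no exact method.

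The only summary that 7.2.1.8 names is a different quantity: "Summary statistics of blood glucose level (mg/dL) will be provided by treatment arm at each time point for patients reporting severe hypoglycemia".

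SAP 4.8 records that enrolment was stopped and that "fewer patients compared to the originally planned will be available for the analysis". It makes all analyses descriptive. SAP 10.1 provides for output that fails: "Missing descriptive statistics or p-values which cannot be estimated are reported as" a dash.

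**The concern.** A Cox hazard ratio needs episodes in both arms. With none in one arm, the partial likelihood has no maximum, and the estimate that software prints depends on where the iterations stop.

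The SAP anticipates sparse or awkward data for its other secondary endpoints. Proportions switch to Fisher's exact test and continuous measures to the Mann-Whitney test. The episode count is the endpoint most exposed to small numbers, and it has no such alternative.

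In a descriptive analysis, the episodes, the time over which they were observed and an interval for the rate are the result. If the hazard ratio is degenerate and 7.2.1.8 is followed as written, the reader may get a hazard ratio of 0 or infinity, limits from 0 to infinity, and glucose values for the patients affected.

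**Working it through.** The plan states no episode rate, expected count or power for this endpoint, so there is no figure to reproduce.

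**Inputs**
- Allocation 2:1 (SAP 3.4). The planned 75 patients (SAP 3.3) give 50:25.
- Final sample size: not stated. 24:12 and 16:8 are assumed as smaller cases.
- Follow-up: 18 months from first dose (SAP 3.1), taken as 1.5 years for every patient.
- Episode rate: not stated. 0.02 to 0.20 per patient-year is assumed, Poisson and equal in both arms.

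**1. The planned model with an empty arm.** Let all k episodes be on placebo, with twice as many ladarixin patients at risk throughout. Up to a constant, the log partial likelihood is −k·ln(1 + 2e^b). It rises without end as b falls, so there is no finite estimate. The information is k·2e^b/(1 + 2e^b)², and the standard error is 1/√information. For k = 4:

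| b | SE | Wald p (two-sided) |
|---|---|---|
| −5 | 4.4 | 0.25 |
| −10 | 52 | 0.85 |
| −20 | 7,788 | 0.998 |

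The hazard ratio tends to 0 and its Wald limits to 0 and infinity. Only the 2:1 ratio enters, so all three sample sizes give the same result. With the placebo arm empty, the hazard ratio tends to infinity instead.

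**2. What survives in the same model (0 vs 4).**
- Likelihood ratio: 2 × 4 × ln 3 = 8.79, two-sided p = 0.003.
- Score: (4 × 2/3)² / (4 × 2/9) = 8.0, two-sided p = 0.005.
- Inverting the likelihood ratio, 8·ln(1 + 2h) = 3.84 gives an upper hazard-ratio limit of 0.31. The code does not ask for it.

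**3. Alternatives that stay finite (0 vs 4, patient-time 2:1).**
- Exact conditional test: one-sided p = (1/3)⁴ = 0.012. For the upper limit, (1 − π)⁴ = 0.025 gives π = 0.602, so the rate ratio limit is 0.602/(2 × 0.398) = 0.76. The result is a rate ratio of 0 (95% CI 0 to 0.76).
- Firth's penalty on the same counts: rate ratio 0.056 (95% CI 0.0004 to 0.52).
- Rates at 50:25: ladarixin 0/75 patient-years, exact upper limit 3.69/75 = 0.049 per year; placebo 4/37.5 = 0.107 per year (exact 95% CI 0.029 to 0.273).

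**4. How often exactly one arm is empty.** With p = exp(−rate × 1.5 × n) for each arm, the chance is p_L + p_P − 2·p_L·p_P:

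| Rate per patient-year | 50:25 | 24:12 | 16:8 |
|---|---|---|---|
| 0.02 | 48% | 51% | 43% |
| 0.05 | 17% | 44% | 52% |
| 0.10 | 2% | 18% | 34% |
| 0.20 | under 1% | 3% | 10% |

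Example, 24:12 at 0.05: p_L = e^−1.8 = 0.165 and p_P = e^−0.9 = 0.407, giving 0.165 + 0.407 − 2 × 0.165 × 0.407 = 0.44. The smaller arm is empty more often. Here placebo alone is empty with probability 0.407 × 0.835 = 0.34, and ladarixin alone with probability 0.165 × 0.593 = 0.10. At 16:8 and 0.02, both arms are empty in a further 0.619 × 0.787 = 49%, and then the model has no events to fit.

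**5. Counts and rates in the text.** SAP 7.2 promises descriptive statistics for all secondary endpoints as detailed in its subsections, and 7.2.1.8 details only glucose values. SAP 8.1 adds numbers of events to the adverse event tables by organ class and preferred term, whereas this endpoint is derived from the diary forms (SAP 9.1, Table 3). Patient-time and an episode rate by arm appear in neither document.

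**The case against.** The strongest case against is that the SAP is less bare than 7.2.1.8 suggests. Each stronger reading below goes further than the documents allow.

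- **That an empty arm leaves no p-value.** Only the Wald p-value fails, and the SAP does not say which p-value it will report. At 0 vs 4 the likelihood-ratio and score tests both detect the difference. What stands is that neither, as coded, brings a usable estimate or interval.
- **That this is the main hypoglycaemia safety comparison.** It is listed as a secondary efficacy endpoint. SAP 8.1 has Kaplan-Meier estimates and a log-rank test of time to onset, which survive an empty arm, and SAP 7.2.1.6 has a proportion endpoint that includes absence of severe episodes, with a Fisher alternative. None of these measures the number of episodes.
- **That no count will be produced at all.** The general promise in SAP 7.2, the listings promised in SAP 4.1 and the event numbers in SAP 8.1 prevent that conclusion, and the mock shells cannot be checked.
- **That a robust variance could make one chance episode look decisive.** Protocol 9.5.2.2 does plan the comparison "using an Andersen-Gill analysis with robust sandwich-type variance estimate", but SAP v3.0 replaces this with model-based variance, so that output is not part of the current plan.
- **That an empty arm is likely.** The serious events listed for the earlier trial (Protocol 2.4.3) include no hypoglycaemia. But the definition of a severe episode in Protocol 4.1 does not require seriousness, so this is weak evidence of rarity.

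The stakes are also limited. No formal testing is planned, and a degenerate hazard ratio would be visible as such.

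**Conclusion.** The point holds in a limited form, as a cheap improvement. The only specified between-arm analysis of the number of episodes gives an uninformative hazard ratio and Wald interval whenever one arm is empty. That part follows from the likelihood and needs no assumption about rates.

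How often it would happen does rest on assumptions: equal Poisson rates, 1.5 years for every patient and an unknown final sample size. Over the assumed range the chance runs from about one half to under 1%. With enrolment stopped early and 2:1 allocation it is a realistic contingency to plan for, and the documents support no firmer statement.

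The gap in description is narrower than a missing count. Section 7.2.1.8 names none, and patient-time and a rate by arm are named nowhere in the two documents.

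**What to change.** In SAP 7.2.1.8, add a table by arm, cumulative to Month 6, 12 and 18, with:
- episodes;
- patients with at least one episode;
- patient-years;
- rate per patient-year with an exact Poisson 95% CI.

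For the comparison, either add the FIRTH option to the MODEL statement in Appendix 12.2 and request profile-likelihood limits, or report the exact conditional rate ratio with its interval. State which p-value, if any, will be shown, and that with no episodes in either arm only the table is reported.

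The cost is one paragraph, one small table and one or two SAS options, with no new data. Firth's penalty shrinks the estimate slightly. The exact ratio assumes Poisson episodes and so treats repeat episodes in one patient as independent. Showing the number of patients with at least one episode beside it lets the reader judge that.

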# PPD

Document Version	Changes Made	Document Date
	
The main sections impacted are:
 

• Section Efficacy endpoints: one single final analysis has been planned after DB lock;

• Section 4.3: removal of the primary estimands;

• Section 4.4 and 4.8: modified to reflect the reduction in the efficacy analyses;

• Section 4.5 and 5.5: given the reduced sample size compared to the planned one, some analyses (subgroup analysis and Kaplan-Meier curve for the time-to-discontinuation analysis) have been removed from the statistical plan;

• Section 7.1 and 7.2: given the reduced sample size compared to the planned one, some advanced analyses (logistic regression, multiple imputation approaches, sensitivity analysis) have been removed from the statistical plan;

• Sections 12.1: clarifications.

• Section 6 regarding Compliance has been updated

• CGM parameters units have been added

• Severe Hypoglycemia derivation has been updated in section 9.1

• Additional information regarding Reason for discontinuation summaries has been added in 5.1 section.

• Additional details regarding stop enrollment and changes in planned analysis has been added

• HLA DR-DQ haplotypes will be only listed

• Section 7.2.1.6 updated

• Details and correction of the Cox model

• Derivation of severe hypoglycemia events has been added

• Number of AEs added in AE summaries

	

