# PPD

- no formal hypothesis testing will be performed;
- all analyses will be descriptive in nature;
- no advanced analytical methods will be applied, specifically:
  - Primary endpoint no more analyzed by means of logistic regression model: comparison between treatment arms performed by means of a Chi-square test at each time point.
  - No multiple imputation approaches to manage potential missing data;
- no sensitivity analyses will be performed;
- no sub-group analyses will be performed;

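### The SAP replaces the protocol's robust variance for recurrent severe hypoglycaemia with a model-based one and does not state or justify the change; if episodes cluster within patients, the interval can be too narrow

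*SAP*

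**What the plan says.** Protocol 9.5.2.2 (Secondary analyses) says that the effect on cumulative severe hypoglycaemic events will be assessed "using an Andersen-Gill analysis with robust sandwich-type variance estimate".

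SAP 7.2.1.8 keeps the endpoint and the model but changes the variance: "The Andersen-Gill intensity model with model-based variance will be utilized". The code in SAP 12.2 opens with "proc phreg data=dataset covm", has treatment as its only model term and has no patient `id` statement. A note under it explains that the `covm` "option specifies that the model-based covariance matrix will be used". The same appendix sets out several rows per patient: one ending at each recurrence and a last one ending at the end of follow-up.

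SAP section 1 sends the reader to 4.8 for changes to the planned analysis caused by the premature closure. Section 4.8 covers the single final analysis, the absence of formal testing, the replacement of logistic regression, and the removal of multiple imputation, sensitivity and subgroup analyses. It also says that "all analyses will be descriptive in nature". It is silent on this variance. The revision history for version 3.0 has one related entry: "Details and correction of the Cox model".

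**The concern.** With treatment as the only covariate, the model-based variance of the Andersen-Gill estimate is valid only if all patients in an arm share the same episode intensity, so that a patient's earlier episodes say nothing about later ones. If some patients are more prone to severe hypoglycaemia than others, each repeat episode carries less information than the model credits. The standard error is then too small. The sandwich variance clustered on patient does not need that assumption, and it is what the protocol planned.

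At stake are the hazard-ratio interval and nominal p-value for one secondary endpoint. With no formal testing, the interval is what a reader uses to judge uncertainty, so it should not look more precise than the data allow. The Kaplan-Meier and log-rank analysis of time to onset (SAP 8.1) and the proportion with HbA1c below 7% and no severe event (SAP 7.2.1.6) do not use repeat episodes and are unaffected.

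**Working it through.** **Is it a slip?** No. The SAP text, code and code note all agree on the model-based variance and all differ from the protocol. Early closure does not explain the change: the Andersen-Gill model is retained, and the robust option is no harder to run.

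**Is there a figure to reproduce?** No. The documents give no rate, hazard ratio or standard error for this endpoint.

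**Inputs from the documents:** 2:1 allocation, 75 patients planned (about 50:25), 18 months' follow-up. **Assumed:** episode rate, between-patient dispersion and achieved sample size (20:10 is used as a smaller example).

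**Formulas.** Let m be the mean number of episodes per patient, θ the gamma frailty variance, and E1 and E0 the total episodes per arm. With common follow-up and treatment only, the Andersen-Gill estimate is approximately the log rate ratio, and

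- model-based variance = 1/E1 + 1/E0
- clustered sandwich variance = sum over arms of Σ(Nᵢ − mean)² / E²
- true SE ≈ √(1 + θm) × model-based SE

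A check against one start-stop fit gave a model-based SE of 0.237 (formula 0.237) and a robust SE of 0.423 (formula 0.436).

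**Worked example.** Take 50:25, m = 0.5, θ = 3. Expected episodes are 25 and 12.5. The model-based SE is √(1/25 + 1/12.5) = √0.12 = 0.346. The true SE is about √(1 + 1.5) × 0.346 = 1.58 × 0.346 = 0.548. Around a hazard ratio of 1, the model-based 95% interval is exp(±1.96 × 0.346) = 0.51 to 1.97. An interval using the true SE is exp(±1.96 × 0.548) = 0.34 to 2.93.

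**Simulated coverage of the nominal 95% interval**, no treatment effect, 40,000 replicates per cell, trials with events in both arms (model-based / robust, %):

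| Patients | m over 18 months | θ = 0 | θ = 1 | θ = 3 | θ = 6 |
|---|---|---|---|---|---|
| 50:25 | 0.15 | 97.5 / 97.4 | 96.7 / 97.2 | 94.6 / 96.6 | 91.7 / 95.9 |
| 50:25 | 0.5 | 95.6 / 94.6 | 90.0 / 93.7 | 80.3 / 92.3 | 70.2 / 90.6 |
| 50:25 | 1.5 | 95.0 / 94.0 | 79.2 / 93.4 | 60.4 / 91.8 | 47.3 / 89.7 |
| 20:10 | 0.15 | 99.3 / 98.6 | 98.9 / 98.4 | 97.6 / 98.1 | 95.5 / 97.6 |
| 20:10 | 0.5 | 97.1 / 95.5 | 93.5 / 94.5 | 86.4 / 92.8 | 79.0 / 91.4 |
| 20:10 | 1.5 | 95.4 / 92.7 | 80.0 / 91.3 | 62.4 / 87.9 | 51.2 / 84.5 |

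Here m = 0.15 and 1.5 correspond to 0.1 and 1.0 episodes per patient-year (m / 1.5 years).

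**Second simulation set** (20,000 replicates, θ = 1 to 4), model-based against robust:

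- 50:25, 0.3-1.0 per patient-year: coverage 55-91% against 91-94%. Nominal one-sided 5% error is 8.8-25.4% against 5.6-6.3% in the tail with fewer events on ladarixin, and 7.5-27.5% against 6.0-9.0% in the other tail.
- 50:25, 0.1 per patient-year: coverage 93.7-96.7% against 96.3-97.2%. One-sided error is 6.6-9.9% against 5.4-6.2% in the first tail and 1.5-3.0% against 1.8-2.4% in the second.
- 20:10, 0.3-1.0: coverage 57-94% against 87-95%.
- 20:10, 0.1: coverage is above 96% with both. The empirical SD is 0.77-0.85 times the model-based SE, and 29-37% of trials have an arm without events.
- 50:25, 0.05: model-based coverage is 97.4-98.5%, so there is no undercoverage.

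**The case against.** Four points weigh on the other side.

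First, the switch is not hidden. It is stated in 7.2.1.8 and explained in 12.2, and the revision history has an entry on the Cox model. Section 4.8 is framed as changes due to early closure, and it also leaves out the protocol's repeated-measures models. This stands in part: there is no sign of concealment. But no place says that the protocol's variance was replaced, or why.

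Second, the large losses need at least about 0.3 episodes per patient-year together with real clustering, and nothing in the documents supports such a rate. The event definition is strict, patients have preserved C-peptide, and enrolment stopped early. With few patients and rare events the model-based SE is not too small: at 24:12 and 0.1 per patient-year, for example, its coverage is 96.5-98.4%. This stands, and it makes the size of the harm conditional.

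Third, the plain sandwich is liberal with few patients. In the table it falls to 84.5% at 20:10, and without clustering at m = 1.5 it covers 92.7% against 95.4% model-based. This also stands, but that loss is small next to the model-based loss when episodes do cluster.

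Fourth, this is one of ten secondary endpoints, everything is descriptive, and the result is not among the planned graphs. That limits the consequence. It does not make an over-precise interval acceptable.

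**Conclusion.** The concern holds. SAP and protocol specify different variances for the same analysis, and the SAP neither names the change as a departure nor gives a reason. That part does not depend on the event rate. The comparison is with the one protocol text supplied; the SAP cites versions 1 and 2 (US only).

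The numerical effect does depend on assumptions. With clustering and episodes that are not very rare, the model-based interval undercovers badly while the robust one stays much closer to 95%. At about 0.1 episodes per patient-year the difference is small at 50:25. At lower rates, or with few patients and rare events, there is no undercoverage. Without clustering the choice barely matters at 50:25. The case for changing is that the robust option costs about one coverage point or less there and guards against large losses if episodes cluster. The plan should be changed, but this concerns a descriptive secondary analysis and does not touch the primary endpoint.

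**What to change.** In SAP 7.2.1.8, specify a robust sandwich variance clustered on patient. In 12.2, replace `covm` by `covs(aggregate)` and add an `id` statement for the patient identifier. Both parts are needed, because the clustering comes from aggregating rows within patient. If the model-based variance is kept, list the change and its reason in 4.8.

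Either way, report for each arm the number of patients with at least one episode and the total number of episodes, so that clustering and sparse data are visible. SAP 7.2.1.8 already summarises glucose values in patients reporting severe hypoglycaemia, so part of this may already be in the outputs.

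The cost is a few words of text, two lines of SAS and two counts per arm. The downside is the sandwich's own small-sample liberality: at 20:10 in the most clustered scenario of the second simulation set, two-sided error reached about 13%, against about 43% model-based. Its interval should be read with caution if the achieved sample is small, and neither variance helps if an arm has no events.
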